5 ANALYSIS SETS

In accordance with International Conference on Harmonization (ICH) recommendations in guidelines E3 and E9, the following analysis sets will be used for the analyses.

This SAP includes the data analysis for the primary study period which is defined as 1-year post first study drug injection. Certain data summary will consider analysis windows as specified in relevant sections. The long-term follow-up period is not covered by this SAP.

5.1 Full Analysis Set (FAS)

The Full Analysis Set (FAS) consists of all randomized subjects who received at least one dose of randomized study drug and who have at least one post dose viral load assessment within 1-year post first injection by central laboratory.

Specifically, the following will lead to a subject's exclusion from the FAS:

- Did not take study drug , or
- Had no viral load assessment by central laboratory after first study drug injection

The FAS will be the primary analysis set for efficacy analyses and for summaries of selected demographic and baseline characteristics. For this population, data will be analyzed by the treatment group that patients were randomized to.

5.2 Safety Analysis Set (SAF)

The Safety Analysis Set consists of all randomized subjects who received at least one dose of study drug. For the SAF, data will be analyzed according to the study medication that subjects received as the first dose even if it differs from what they were randomized to.

5.3 Immunogenicity Analysis Set (IAS)

The Immunogenicity Analysis Set (IAS) will include subjects who received randomized study drug and for whom at least one post-transplant immunogenicity measurement is available.

The IAS will be used for analyses of the immunogenicity data.

6 ANALYSIS VARIABLES

6.1 Efficacy Endpoints

6.1.1 Primary Efficacy Endpoint

Incidence of CMV viremia (defined as plasma viral load of ≥ 1000 IU/mL by central laboratory assay) through one year post first Study Drug injection is the primary efficacy endpoint.

6.1.2 Secondary Efficacy Endpoints

Secondary efficacy endpoints are: :

- Proportion of subjects with Adjudicated CMV-associated disease including CMV syndrome and CMV tissue-invasive disease.
- Proportion of subjects with plasma viral load \geq the lower limit of quantification [LLOQ] assessed by central laboratory.
- Proportion of subjects who took Adjudicated CMV-specific antiviral therapy for the treatment of CMV viremia or disease.
- Proportion of subjects with graft survival.

6.1.3 Exploratory Efficacy Endpoints

- Number of patients with at least one opportunistic infections other than CMV
- Time to first CMV viremia (defined as plasma viral load of ≥ 1000 IU/mL by central assay) through one year post study first Study Drug injection.
- Time to first adjudicated CMV disease, including CMV syndrome and CMV tissue-invasive disease, through one year post first Study Drug injection.
- Number of episodes of CMV viral load of ≥ 1000 IU/mL by central assay through one year post first Study Drug injection.
- Peak CMV viral load through one year post first Study Drug injection.
- Viral load area under the curve (AUC) adjusted for duration through one year post first Study Drug injection.
- Number of episodes of adjudicated CMV-associated disease, including CMV syndrome and CMV tissue-invasive disease, through one year post first Study Drug injection.

- Proportion of subjects with viral resistance to ganciclovir or valganciclovir through one year post first Study Drug injection as determined by central laboratory assay.
- Proportion of subjects with biopsy-proven (T or B cell) acute rejection (BPAR) (Banff 2007 Grade \geq 1) through one year post first Study Drug injection.
- Estimated glomerular filtration rate (eGFR) at the last study visit calculated using the 4 variable MDRD formula.
- Proportion of subjects with clinically treated acute graft rejection through one year post first Study Drug injection.

6.1.4 Immunogenicity Variables

An indicator of immunogenicity elicited by the vaccine is predicted to be an increase in gB-specific antibody levels and the T-cell response to pp65 protein over time compared with the placebo group.

Two immunogenicity assessments will be performed:

1. T-cell response to viral protein pp65 using cultured ELISpot .
2. Antibody response to gB antigen using an ELISA-based platform.

Assessments will be done from peripheral blood mononuclear cells (T-cells) or serum samples (antibody) isolated over the course of the trial. Time points of the assessments are as follows:

Dose 1, Post Dose 2, Dose 3, Post Dose 4, Dose 5, and End of Study Visit:

- Samples for T-cell assays will not be collected if the Absolute Lymphocyte Count (ALC) is known to be $\leq 500 \text{ mm}^3$ by local or central laboratory measurement.
- If the visit coincides with a study drug administration, the sample will be drawn prior to injection.

Further details will be available in the Laboratory Manual.

6.1.5 Resource Utilization and Patient Reported Outcomes

Additional assessments include the following patient reported outcome measures and resource utilization.

- EuroQol (EQ-5D)
- Kidney Transplant Questionnaire (KTQ)
- Short Form Health Survey version 2 (SF-12v2)
- Health Economic Assessment (HEA)

The EQ-5D, Kidney Transplant Questionnaire (KTQ) and the SF-12 v2, should be completed by the subject prior to any other study assessments or visit procedures. Subjects should complete these assessments in the following order: EQ-5D first, KTQ second, SF-12 last. For all three patient-reported outcome measures, i.e., EQ-5D, KTQ, SF-12, the answers must come from the subject. If the subject is unable to fill out the questionnaire, the assessment should not be performed. If the subject is unable to answer an individual question, the rest of

the questionnaire should still be completed. The questionnaires will be provided in the local language of the subject.

Health economic information will be collected for subjects through one year post first study drug injection.

6.2 Safety Variables

Safety will be assessed by evaluation of the following variables:

- Treatment-emergent adverse events
- Clinical laboratory variables
- Vital signs (systolic and diastolic blood pressure, pulse rate, respiratory rate, temperature, and weight)
- Physical examination.

6.3 Pharmacokinetic Variables

Not applicable.

6.4 Pharmacodynamic Variables

Not applicable.

7 STATISTICAL METHODOLOGY

7.1 General Considerations

All statistical analyses and summary information will be generated according to this analysis plan and any deviations from this plan will be documented in the clinical study report. Any numerical rounding should be performed at the end of calculations. The p-values will be displayed with 3 decimal places. Statistical significance will be determined prior to rounding the p-value.

For continuous variables, descriptive statistics will include the number of subjects (n), mean, standard deviation, median, minimum and maximum. Frequencies and percentages will be displayed for categorical data. Percentages by categories will be based on the number of subjects with no missing data thus the percentages will add up to 100%. Baseline will be the last non-missing value on or prior to first study drug unless otherwise specified.

All efficacy comparisons will be tested at the 1-sided 0.05 significance level. Confidence intervals for efficacy estimates, if provided, will be constructed at 2-sided 90% level.

All data processing, summarization, and analyses will be performed using SAS® Version 9.1.3 or higher on Unix.

This SAP includes the data analysis for the primary study period (ie, 1-year post first study drug injection) which is defined as data collected through day 380 (=365+14+1 day). Certain data summary will consider analysis window as specified in each section. The long-term follow-up period is not covered by this SAP and will be managed in a separate SAP.

7.2 Study Population

7.2.1 Disposition of Subjects

The following subject data will be presented:

- Number of subjects with informed consent, discontinued before randomization, and randomized;
- Number and percentage of subjects randomized in each analysis set, by treatment group;
- Number and percentage of subjects completed and discontinued treatment, by reason for treatment discontinuation for randomized subjects, by treatment group;
- Number and percentage of subjects completed and discontinued the study, by reasons for study discontinuation for randomized subjects and by treatment group;

7.2.2 Protocol Deviations

Protocol deviations as defined in the study protocol (Section 8.1.6 Protocol Deviations) will be assessed for all randomized subjects. The number and percentage of subjects meeting any criteria will be summarized for each criterion and overall, by treatment group and total as well as by study site. Subjects deviating from a criterion more than once will be counted once for the corresponding criterion. Any subjects who have more than one protocol deviation will be counted once in the overall summary. A data listing will be provided by site and subject.

The protocol deviation criteria will be uniquely identified in the summary table and listing. The unique identifiers will be as follows:

- PD1 - Entered into the study even though they did not satisfy entry criteria,
- PD2 - Developed withdrawal criteria during the study and was not withdrawn,
- PD3 - Received wrong treatment or incorrect dose,
- PD4 - Received excluded concomitant treatment.

7.2.3 Demographic and Medical History

Demographic and other baseline characteristics will be summarized by descriptive statistics for FAS and SAF populations.

Number and percentage of subjects randomized in each country and site will be presented by treatment group for the SAF.

Descriptive statistics for age, weight, body mass index (BMI), BMI categories (<25, 25 to <30, and ≥ 30 kg/m²), height at study entry, and the demographic categories defined below will be presented.

Demographics	Categories
Ethnicity	Not Hispanic or Latino
	Hispanic or Latino
Race	White
	Black
	Other
Age group	< 65 years
	≥65 years
Gender	Female
	Male

Medical history is coded in MedDRA, and will be summarized by System Organ Class (SOC) and Preferred Term (PT), by treatment group for the SAF.

7.2.4 Previous and Concomitant Medications

Previous medications are coded with WHO-DD, and will be summarized by therapeutic subgroup (ATC 2nd level) and chemical subgroup (ATC 4th level) and preferred WHO name by treatment group for the SAF.

A drug stopped before or on the day of the first study drug injection will be defined as previous medication. And a drug started within the primary study period will be defined as concomitant medication. As with previous medication, concomitant medication will be summarized for each treatment group by therapeutic subgroup (ATC 2nd level) and chemical subgroup (ATC 4th level) and preferred WHO name. Subjects taking the same medication multiple times will be counted once per medication and investigational period. A medication which can be classified into several chemical and/or therapeutic subgroups is presented in all chemical and therapeutic subgroups.

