5.1.1 Dose/Dose Regimen and Administration Period

Doses will be given at the following time points:

- Dose 1 at Day 30 \pm 3 days, post transplant.
- Dose 2 at Day 60 (\pm 5 days)
- Dose 3 at Day 90 (\pm 5 days)
- Dose 4 at Day 120 (\pm 5 days)
- Dose 5 at Day 180 (\pm 5 days)

An injection should not be given if, 1) the subject has been on an anticoagulant within 5 half-lives prior to the injection or there is any other contraindication to an intramuscular injection or 2) has a Temperature \geq 100.4° F or 38° C (per NCI Grade 1.) Low dose anticoagulants that are used for prevention of deep vein thrombosis are allowed. Immunosuppressive agents used to prevent rejection should be given according to the standard of care at the center and taking note of the list of prohibited medication.

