Adjudication Committee	A group of clinical experts who will create specific, standardised event definitions for each suspected events of interest including all cases of CMV syndrome, CMV tissue-invasive disease and CMV-specific antiviral therapy.
Baseline	Baseline is the time point prior to the first dose of randomized study drug. Visit 2 is considered the Baseline Visit in this study. The last measurements / evaluation prior to the first dose of randomized therapy is considered the baseline measure/evaluation.
CMV Viremia	Presence of CMV in the blood.
Double-Blind	Neither the subjects of the trial nor the persons administering the trial know the true treatments.
End of Study	The point in time when the last protocol-defined assessment has been completed (end of the Long-term Follow-up Period).
End of Treatment	The point in time when the subject receives the last dose of study drug.
Enrollment	The point in time when the subject signs the informed consent.
Evaluable Subject	A subject who meets all inclusion criteria and does not meet any exclusion criteria and who has received at least one injection of study drug.
Hard Lock	Hard lock of a study database occurs after all issues discovered in final data review have been resolved and it is expected that no more changes to the study database will occur. Only after hard lock are treatment assignments unblinded.
Independent Statistician	The statistician who is not part of the study team
Investigational Period	The time between the first dose of study drug (Visit 2) through one year post first dose of study drug (Visit 13).
Long-term Follow-up Period	The period of time from the Day 395 Visit (Visit 13) through the completion of the 4½ year additional safety follow-up.
Long-term Follow-up Withdrawal	A subject who completes the Primary Study Period but does not complete the Long-term Follow-up Period for any reason.
Preemptive Therapy	A therapeutic treatment regimen where treatment for an infection/disease is initiated only after it is detected/confirmed.
Primary Study Period	From first study drug injection (Day 1) to the time of early termination or 1-year post first study drug injection (Day 380), whichever is first.
Primary Study Withdrawal	A subject who is randomized but does not complete the Primary Study Period for any reason.
Protocol-defined CMV viremia	CMV plasma viral load ≥ 1000 IU/mL as assessed by the central laboratory.

Terms	Definition of terms

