† Days in Study Schedule when CMV and Regular Visit can be performed together per Protocol. The overlap used assumes the visits are done exactly on the specified visit day from Transplant. If +/- window is used for a dosing visit, the corresponding follow up visit should take place within the 14 days +/-3 from the date of the Study Drug dose. Visits 10 & 11 must be at least 7 days apart.

Tables 1 and 2 Footnotes:

1. Screening may be done from Day -14 up to Randomization, Day 30. Screening and Randomization can take place on the same day as long as Clinical Labs are drawn and results are available on the day of Randomization. If Screening is done > 3 days prior to Randomization, Clinical Labs, urinalysis and urine protein: creatinine ratio must be repeated and available prior to Randomization. Subjects may be rescreened due to rescheduling of transplant surgery provided the screening procedures are repeated and fall within the -14 day to + 30-day window relative to the Day of Transplant. First study drug dosing must take place within 24 hours of Randomization.
3. The date of transplant (day of skin closure) defines Day 0 and all visit days are relative to Day 0.
4. Subjects are to receive prophylactic valganciclovir or ganciclovir starting within 10 days post transplant through the Day of Randomization to prevent CMV disease. (The subject can miss up to two doses of valganciclovir or ganciclovir during this time period for any reason). Valganciclovir or ganciclovir dose is to be given per the package insert. The subject will then continue to receive CMV-specific AVP until 100 days post transplant. Subjects can have CMV-specific AVP interrupted, dose adjusted or replaced by other CMV-specific AVP per standard of care after the Day Randomization if renal function is compromised, there are toxicities related to the administration of the AVP, or for any other medically indicated reason.
5. Informed consent must be obtained prior to the performance of any study-related procedure.
6. Subjects will be assigned a subject number for use throughout the study at the Screening Visit via the Interactive Response Technology (IRT) system.

Footnotes continue on next page

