7.9 Handling of Missing Data, Outliers, Visit Windows, and Other Information

7.9.1 Missing Data

In the analysis of the primary endpoint, subjects who are lost to follow-up will be imputed as having viremia. Otherwise, viremia will not be imputed. Only observed viral loads from central labs meeting the definition of viremia will be counted.

Time to event variables will be considered censored at the time of the last assessment. Time to the first protocol-defined CMV viremia will be considered censored at the time of the last recorded central laboratory CMV measurement.

The start and stop dates of AEs and concomitant medication will be imputed to allocate the concomitant medication and AEs to a treatment group, in addition to determining whether an AE is/is not treatment emergent. Listings of the AEs and concomitant medications will present the actual partial dates; imputed dates will not be shown.

In case of missing partial start and stop dates for concomitant medications, the following rules will be used:

If start date is missing or partial:

- if month is missing, use January
- if day is missing, use the first day of the month under consideration
- if year is missing, use year of the informed consent date
- if entire date is missing, use informed consent date

If stop date is missing or partial:

- if month is missing, use December
- if day is missing, use the last day of the month under consideration
- if year or the entire date is missing, set to December 31st, 2099

If the imputed start date is after the stop date, then the imputed start date will be one day prior to the stop date.

For AEs, a missing or incomplete onset date will be imputed according to the following conventions for the purpose of defining TEAE.

- 1) Missing year, the AE will be count as TEAE
- 2) Missing month, the AE will be counted as TEAE if the year is equal to the consent year or one year later.
- 3) Missing date, using the last date of the month to determine TEAE.

No imputation of missing data for other variables will be done.

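### SAP 7.2.4 places a medication record that begins before the first injection and continues past it in neither medication table, so maintenance immunosuppression has no complete by-arm summary

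*SAP*

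**What the plan says.** SAP 7.2.4 sorts medications with two one-sided tests. The first looks only at the stop date: "A drug stopped before or on the day of the first study drug injection will be defined as previous medication". The second looks only at the start date: "And a drug started within the primary study period will be defined as concomitant medication". The SAP's List of Key Terms runs the primary study period "From first study drug injection (Day 1) to the time of early termination or 1-year post first study drug injection (Day 380"); the earlier of the two ends it. There is no third category.

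SAP 7.9.1 fills in incomplete dates. A wholly missing start date becomes the informed consent date. For stop dates the rule is: "if year or the entire date is missing, set to December 31st, 2099".

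On timing, subjects are randomized at Day 30 ± 3 after transplant, and "First study drug dosing must take place within 24 hours of Randomization". For antiviral prophylaxis, "Subjects are to receive prophylactic valganciclovir or ganciclovir starting within 10 days post transplant through the Day of Randomization to prevent CMV disease", and then "The subject will then continue to receive CMV-specific AVP until 100 days post transplant". Protocol 5.1.1 says of maintenance treatment: "Immunosuppressive agents used to prevent rejection should be given according to the standard of care at the center". Protocol 5.1.3.2 requires Pneumocystis prophylaxis to be initiated in all participants. Protocol 5.1.3.4 collects all medications, immunosuppressants included, from 14 days before transplant through Visit 13.

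**The concern.** The two tests leave a gap. A drug begun before the first injection and still being taken afterwards has not stopped in time to be *previous*, and it began too early to be *concomitant*. In many trials such drugs are a minority. Here dosing begins a month after transplant, so background treatment begun around transplant and continued is the usual case.

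The protocol's own background section attributes susceptibility to CMV in transplant recipients to the immunosuppression used against rejection, and the primary endpoint is CMV viremia. With about 70 subjects per arm, and stratification only on ATG use and donor type, a reader of the report will want to compare the arms on background immunosuppression during the efficacy period. If the rule is programmed as written, the medication tables will not give a complete comparison, although the data are collected.

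**Working it through.** The plan states no figure to reproduce. The check applies the definitions literally.

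**Rules as coded**
- *Previous*: stop ≤ Day 1.
- *Concomitant*: Day 1 ≤ start ≤ Day 380.

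**Study day.** For transplant day t and first injection on transplant day d, study day = t − d if t < d, and t − d + 1 if t ≥ d. This assumes no Day 0. The SAP does not say, and its screening start of −43 (= −14 − 30 + 1) would imply one. Counting a Day 0 shifts the pre-injection days by one and changes no classification in the table below.

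**Worked cases across the randomization window**

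| Record | d = 27 | d = 30 | d = 33 | Previous? | Concomitant? |
|---|---|---|---|---|---|
| Immunosuppressant from transplant Day 0, ongoing (start assumed) | −27 onward | −30 onward | −33 onward | No | No |
| CMV prophylaxis, transplant Day 10 to 100 | −17 to 74 | −20 to 71 | −23 to 68 | No | No |
| Drug from transplant Day 0, stopped on the injection day | −27 to 1 | −30 to 1 | −33 to 1 | Yes | No |
| Drug started and stopped on the injection day | 1 to 1 | 1 to 1 | 1 to 1 | Yes | Yes |
| New record starting on study Day 20, ongoing | 20 onward | 20 onward | 20 onward | No | Yes |

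**All date pairs.** Let the start run over −43 to −1 and 1 to 380, and the stop from the start day up to 381 (381 standing for after the period). The number of pairs is 424 + 423 + … + 2 = 90,099. Those in neither category are exactly the pairs with start before Day 1 (43 values) and stop after Day 1 (380 values): 43 × 380 = 16,340. One pair, start and stop both on Day 1, is in both. These counts show where the rule fails; they do not estimate the share of medication records affected.

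**Imputation.** Consent precedes dosing, so a wholly missing start date is placed before Day 1. If the stop date is also missing it becomes 2099, and the record is in neither table. The imputation rules do not close the gap.

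**Other by-arm summaries in the SAP**
- 7.2.5: antivirals by reason for use, and days on prophylaxis by treatment.
- 7.2.6: ATG use, yes or no.
- 7.4.1.3: subgroups by ATG, alemtuzumab or rituximab use after randomization.
- Maintenance immunosuppressants and Pneumocystis prophylaxis: none outside 7.2.4.

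**The case against.** **Prophylaxis is reported.** A reader might infer that valganciclovir and ganciclovir use goes unreported. It does not. SAP 7.2.5 compares the arms on days of prophylaxis, which is more informative than an ATC count. This stands, and it takes CMV prophylaxis out of the uncovered loss.

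**Immunosuppression is partly covered.** A reader might also infer that the report could show nothing about balance on immunosuppression. That is too strong. ATG before randomization is a stratification factor, ATG use is tabulated, and depleting agents after randomization define subgroups. Listings of concomitant medications are also foreseen, though listings do not compare arms. What remains is maintenance treatment and other continued drugs.

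**Not every continued drug is lost.** The gap applies to a single record that spans Day 1. If a dose change or restart is entered as a new record on or after Day 1, that record counts as concomitant. The documents do not say how such records are split. Coverage would then depend on data-entry practice, which softens the problem without removing it.

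**The 2099 date is not a fault.** A far-future stop date correctly keeps an ongoing drug out of the previous table. The fault lies in the start-only test for concomitant medication.

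**The intent was probably the usual rule.** An overlap definition (taken during the period) may well be what was meant, but the SAP does not state it. The protocol defines the Primary Study Period from signing of consent, and using that definition would repair the rule only in part. A drug begun before consent and continued would still be in neither table, and one begun after consent and stopped before the injection would be in both.

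**Conclusion.** The point holds as a drafting error in a stated rule: followed literally, SAP 7.2.4 gives incomplete medication tables. It is minor. The primary CMH test, the subgroup models, the error rate and the sample size do not use these definitions; only descriptive background tables are affected.

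For CMV prophylaxis, absence from both 7.2.4 tables in nearly every subject follows from the eligibility and prophylaxis requirements, if the course is held as one record, but the information is available through 7.2.5. For maintenance immunosuppression and Pneumocystis prophylaxis, the extent rests on two assumptions that the documents do not settle: that treatment starts at or near transplant, before the first injection, and that it is entered as one continuous record. If both hold, most subjects' maintenance regimens would be missing from the by-arm summaries. If dose changes create new records, some would appear and others would not.

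**What to change.** Replace the two definitions in SAP 7.2.4:
- *Previous*: any drug stopped before the first study drug injection.
- *Concomitant*: any drug taken on or after the first injection through the end of the primary study period, whatever its start date.

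In dates, these are stop < Day 1, and start ≤ Day 380 with stop ≥ Day 1 or ongoing. Every record with a start by Day 380 then meets exactly one definition, so both the gap and the Day 1 overlap close. One consequence is that a drug stopped on the injection day itself moves from previous to concomitant.

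The cost is two sentences and the matching program line. No new data are needed, since start and stop dates are already collected and imputed under 7.9.1. The change can be made before hard lock.
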